9.10 Participant remuneration

All participants will receive a mobile phone and mobile phone credits. In addition, modest, study-appropriate remuneration such as a sarong, canned fish, or soap will be provided at biological sample collection/cognitive assessment points (2, 4, 12, 24, and 52 weeks postnatal).

10. Adverse Event Reporting

As described in *2.6 Serious Adverse Events Committee / Data Safety Monitoring Board*, there will be no Serious Adverse Events Committee or Data Safety Monitoring Board assembled for this study, because no adverse events have ever been reported for thiamine. There is no UL for thiamine because there has never been an adverse event reported from high thiamine intake (1,2), even though over-the-counter supplements in Canada and the United States commonly contain 50 mg thiamine or more. With this, we are confident that there is a low risk of serious adverse events in this study. There are also no clinical outcomes for which to monitor: the primary outcome of the study is a biochemical measure of thiamine status, but results will only be known after study completion. Also, there will be no mid-study data available to examine because all biological samples

will be batch analyzed to decrease assessment variability (in addition to logistic considerations for batch storing and shipping samples).

However, the study will employ a Cambodian medical doctor from the Kampong Thom Operational District to answer medical questions from mothers, and, on an *ad hoc* basis, to investigate adverse events. As described above in *2.6 Serious Adverse Events Committee / Data Safety Monitoring Board*, we do expect 2 – 4 infant death during the study due to events not related to the study.

11. Statistical Analysis

The full statistical analysis plan can be found in **Appendix B**. The primary analyses will be performed on an ‘intention to treat’ basis, where all participants will be analyzed according to their allocated treatment group regardless of compliance. A secondary ‘per-protocol’ analysis will be performed on the subset of women who consumed $\geq 80\%$ capsules over the study period. The parameters of the Emax dose-response curves will be estimated using non-linear least squares models. Separate curves will be fitted for outcomes measured at 4 weeks, 12 weeks, and 24 weeks postpartum. The dose where additional maternal intake of thiamine no longer meaningfully increases milk thiamine concentration, defined as the dose that achieves 90% of the maximum concentration, will be estimated from the fitted curve with standard errors estimated by bootstrapping for calculating 95% confidence intervals.

Comparisons between treatment groups will be performed using linear mixed-effects models to account for repeated measurements and adjusted for randomization strata and levels at 2 weeks postnatal. Interaction tests will be performed to assess whether treatment effects depend on genetic hemoglobin disorder. Missing data will be addressed using multiple imputation to create 100 complete datasets for analysis, with a sensitivity analysis performed on the raw (unimputed) data (68). All analyses will follow a pre-specified statistical analysis plan (see **Appendix B**).

12. Administrative Aspects, and Data Security and Management

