2.6 Serious Adverse Events Committee / Data Safety Monitoring Board

There is no necessity for a Serious Adverse Events Committee or a Data Safety Monitoring Board (DSMB) in the current study because of the absence of potential adverse effects. There is no tolerable upper intake level (UL) for thiamine because there has never been an adverse event reported from high thiamine intake (1,2), even though over-the-counter supplements in Canada and the United States commonly contain 50 mg of thiamine or more. Hence, we are confident that there is a very low risk of serious adverse events in this study related to the intervention.

However, we do expect some infant deaths in our cohort due to other causes. As per the 2014 Cambodian Demographic and Health Survey (CDHS), the rate of neonatal (birth to one month) and infant (birth to one year) mortality was 29 and 11 deaths per 1,000 live births, respectively (3). The majority of neonatal deaths occur in the first 6 days postnatal: in the 4 years preceding the 2014 CDHS data collection, 82% of neonatal deaths occurred in the first 6 days after birth (3). Since this study starts at 2 weeks postnatally, we would expect the mortality rate in our study to lie between 1.67 (neonatal mortality > 6 days postnatal for Kampong Thom = $0.029 \times 0.18 \times 320$) and 3.68 (infant mortality in Kampong Thom = 0.011×320) infant deaths.

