8.4 Breaking of the study blind

Breaking blinding during the study

The master ID list will not be unblinded unless in the unlikely event of an adverse event in the trial. Note that the likelihood of any adverse events is extremely unlikely since there is no UL for thiamine because there have been no reports of adverse effects of excess thiamine intake (1,2,25). If, however, there is a medical emergency and unblinding of a participant is required, our blinding mechanism would allow for only one of the two codes per treatment arm to be revealed (as each treatment arm will have two codes). We would then document and explain to the funding agency and all ethics committees why any premature unblinding occurred.

Breaking the blinding after the study

Once data collection and cleaning is complete, the database will be locked and unblinded treatment codes will be included in the database because a blinded analysis is not possible for estimating dose response curves.

Due to the time-consuming nature of coding video-recorded cognitive assessments, data for the following assessments will not be included in the database before it is locked and unblinded: primary engagement task, secondary engagement task, Visual Paired Comparison Task, and Language Preference Task. Note that the research assistants coding the videos for these assessments will remain blinded.

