HAZARDOUS DECOMPOSITION PRODUCTS	Toxic fumes of carbon monoxide, carbon dioxide, nitrogen oxides and other gases may occur
HAZARDOUS POLYMERIZATION	Will not occur
POSSIBILITY OF HAZARDOUS REACTION	Not established
CONDITIONS TO AVOID	Moisture, sunlight and extreme temperatures

SECTION 11: TOXICOLOGICAL INFORMATION

ACUTE TOXICITY	Oral: Rat: LD50: (mg/kg): 3710 Dermal: Rabbit: LD50: (mg/kg): Not available Inhalation: Rat: LD50: (mg/L/4hr): Not available
SKIN CORROSION/IRRITATION	Due to lack of data the classification is not possible.
SERIOUS EYE DAMAGE/EYE IRRITATION	Due to lack of data the classification is not possible.
RESPIRATORY OR SKIN SENSITIZATION	Due to lack of data the classification is not possible.
GERM CELL MUTAGENICITY	Due to lack of data the classification is not possible. Data from germ cell mutagenicity tests were not found.
CARCINOGENICITY	OSHA THIAMINE HYDROCHLORIDE is not listed. NTP THIAMINE HYDROCHLORIDE is not listed. IARC THIAMINE HYDROCHLORIDE is not evaluated. California Proposition 65 This product does not contain any chemicals known to the State of California to cause cancer, birth defects, or any other reproductive harm.
ADDITIONAL CARCINOGENICITY INFORMATION	Not available
REPRODUCTIVE TOXICITY	Due to lack of data the classification is not possible.
SPECIFIC TARGET ORGAN TOXICITY - SINGLE EXPOSURE	Due to lack of data the classification is not possible.
SPECIFIC TARGET ORGAN TOXICITY - REPEATED EXPOSURE	Due to lack of data the classification is not possible.

ASPIRATION HAZARDS	Based on available data, the classification criteria are not met.
SIGNS AND SYMPTOMS OF EXPOSURE	Not expected to present a significant hazard under anticipated conditions of normal use. Adverse effects with thiamine are rare, but hypersensitivity reactions have occurred, mainly after parenteral doses. These reactions have ranged in severity from very mild to, very rarely, fatal anaphylactic shock.
POTENTIAL HEALTH EFFECTS	Inhalation May be harmful if inhaled. May cause respiratory tract irritation.
	Ingestion May be harmful if swallowed.
	Skin May be harmful if absorbed through skin. May cause skin irritation.
	Eyes May cause eye irritation.

SECTION 12: ECOLOGICAL INFORMATION

TOXICITY	EC50: 48 Hr: Daphnia magna: (mg/L): Not available LC50: 96 Hr: Fish: (mg/L): Not available IC50: 72 Hr: Algae: (mg/L): Not available
PERSISTENCE AND DEGRADABILITY	Not available
BIOACCUMULATIVE POTENTIAL	Not available
MOBILITY IN SOIL	Freely soluble in water.

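### The protocol justifies having no safety committee by a statement that its own Appendix A contradicts, and it describes no uniform collection or by-arm summary of adverse events

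*Combined protocol and SAP*

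**What the plan says.** **The rationale.** On oversight, protocol Section 10 is categorical: "there will be no Serious Adverse Events Committee or Data Safety Monitoring Board assembled for this study". The ground it offers for this is equally unqualified, namely "because no adverse events have ever been reported for thiamine". Section 2.6 opens with "There is no necessity for a Serious Adverse Events Committee or a Data Safety Monitoring Board" and gives the reason as "because of the absence of potential adverse effects". It then supports this with a narrower statement, that "there has never been an adverse event reported from high thiamine intake". Section 10 adds two further reasons: the primary outcome is biochemical, so there is nothing clinical to follow, and batch analysis means that no laboratory results exist during the study.

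**The appended safety sheet.** Section 6.3 (Safety of thiamine doses) points the reader to Appendix A. Section 11 of that data sheet says: "Adverse effects with thiamine are rare, but hypersensitivity reactions have occurred, mainly after parenteral doses". On how serious they were, the same entry adds: "These reactions have ranged in severity from very mild to, very rarely, fatal anaphylactic shock".

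**What is provided for.** Section 10 employs a local doctor to answer mothers' medical questions and to look into adverse events ad hoc. Section 8.4 allows emergency unblinding. Section 12.6 allows early closure if safety data raise concern. Section 9.2 lists what is asked at the fortnightly visits: capsule use, selling or sharing of salt, and infant feeding. The SAP has no adverse-event outcome and no adverse-event table.

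**Expected deaths.** Sections 2.6 and 10 expect 2 to 4 infant deaths and attribute them in advance to causes outside the study.

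**The concern.** There are two separate problems.

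The first is wording. Section 10's reason is absolute, with no limit by route, dose or population, and the document appended as the safety reference says otherwise. An ethics committee reading both is given a rationale that does not agree with its own attachment.

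The second is ascertainment. If events reach the record only when a mother raises them or a doctor happens to be called, the chance of being recorded can differ between women and between health centres, and there is no common denominator. A statement on safety by arm would then have little behind it.

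This matters apart from any toxicity of the capsules. Section 3.1 describes infantile beriberi as arising during exclusive breastfeeding and as rapidly fatal if untreated, and Section 3.7 says poor maternal intake puts such infants at risk. One arm receives 0 mg for 22 weeks. Illness and death by arm are therefore of interest in both directions, and Section 10's remark that there is nothing clinical to monitor fits poorly with the protocol's own background.

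**Working it through.** The core of this point is a comparison of texts. The arithmetic only gives scale.

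**1. The absolute statements against Appendix A.** Section 10 says no adverse event has ever been reported for thiamine, and Section 2.6 says potential adverse effects are absent. Appendix A says reactions have occurred. An unqualified negative is refuted by one documented exception, so the wording of both sections fails. All three are current text in the same document.

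**2. The narrower statements.** Sections 2.6, 3.2, 6.3 (Safety of thiamine doses) and 8.4 also speak of effects of high or excess intake, to explain why no upper intake level exists. Hypersensitivity is not presented in Appendix A as an effect of excess. These statements are not directly contradicted.

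**3. What the reason governs.** In Section 10 the stated reason applies to the two committees. The absence of routine event collection is not presented as following from it; that has to be shown separately, as in step 4.

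**4. Places where events could be captured.**

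| Place | Content described | Uniform event question? |
|---|---|---|
| Section 9.2, fortnightly visit | capsules, salt, feeding | none listed |
| Section 6.4, weekly call | encouragement to take capsules | none listed |
| Section 9.4, questionnaire at 2, 12, 24 and 52 weeks | health information; sleep and postpartum depression named | none named |
| Section 8.5, withdrawal | reason recorded, shown in flow diagram | only for those who leave |
| Section 10, doctor | ad hoc | no |
| SAP Sections 6 and 7 | baseline, compliance, missing data, randomisation errors, efficacy outcomes | no event table |

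Sections 8.4 and 12.6 both depend on adverse events or safety data becoming known, but no routine source of such information is described.

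**5. Expected infant deaths, from the rates in Section 2.6.**
- Lower figure: 0.029 × 0.18 × 320 = 1.67, as stated.
- Upper figure: 0.011 × 320 = 3.52. The protocol prints 3.68, which corresponds to 0.0115 × 320.
- Both versions round to the 2 to 4 of Section 10.

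Section 2.6 gives a neonatal rate (29 per 1,000) above the infant rate (11 per 1,000), although the infant period contains the neonatal one. The labels or figures need checking. I use 2 to 4 as the plan's own expectation; the point does not depend on it.

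**6. Opportunities to ask.** 22 weeks ÷ 2 = 11 visits per dyad, and 11 × 320 = 3,520 visits if nobody leaves. This is a count of visits at which a question could be placed, not a measure of harm or bias.

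**7. What a by-arm table could show.** The three active arms hold 3 × 80 = 240 women. If none had a reaction, the one-sided 95% upper limit for the risk would be 1 − 0.05^(1/240) = 0.0124, or about 1.2%. Very rare reactions could not be excluded, and 2 to 4 deaths across four arms would support description only.

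**The case against.** The strongest case on the other side is that this is loose wording about a very safe vitamin, and most of that stands.

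- **A reader might infer that the capsules carry a material risk of anaphylaxis.** The documents do not support this. Appendix A calls adverse effects rare, ties the reactions mainly to parenteral dosing, calls fatal ones very rare, and expects no significant hazard in normal use. The trial product is oral. The word for mainly does not exclude other routes, but nothing says that a severe reaction followed an oral dose.
- **A reader might infer that the false statement is why monitoring was dropped, or that a committee is needed.** Section 10's reason covers only the committees, other reasons are given beside it, and nothing here requires a committee.
- **A reader might see Section 8.4 as contradicting the expected deaths.** It says "The master ID list will not be unblinded unless in the unlikely event of an adverse event in the trial". Read in context, that concerns events from thiamine, whereas the deaths are expected from other causes. This is imprecise drafting rather than conflicting expectations.
- **The forms have not been seen.** SAP Section 6.3 cites a fortnightly data collection sheet that is not among the documents, and Figure 1 is not shown. One can say that Section 9.2 lists no such question, not that the sheet lacks one.
- **Some information would surface anyway**, through the questionnaire's health items, withdrawal reasons and the doctor. A death recorded as a withdrawal reason should appear in the flow diagram.
- **No stated objective concerns safety**, so no planned conclusion changes.

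What remains is that two sentences disagree with the appended sheet, and that these partial sources do not amount to asking every woman the same thing at the same times and reporting it by arm.

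**Conclusion.** The point holds in a limited form. The unqualified wording in Sections 2.6 and 10 is refuted by Appendix A and must be reconciled with it. That is a correction of the rationale, not evidence of danger from the product.

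Separately, the plan as described has no uniform adverse-event collection and no adverse-event summary in the SAP. Illness short of withdrawal could not be compared across arms, and the view that the infant deaths are unrelated to the study could not be properly examined. The size is modest: no efficacy estimate is affected, the expected deaths number 2 to 4 among 320 infants, and any table would be descriptive.

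The wording conclusion rests on the text alone. The collection conclusion assumes that Sections 9.2 and 9.4 fairly summarise the forms. If the fortnightly sheet already carries a standard event question, only the description in the protocol and the SAP table are missing.

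**What to change.** 1. Reconcile the wording of Sections 2.6 and 10 with Appendix A, so that the reason for having no committee agrees with the appended sheet.
2. Add one standard question to the existing fortnightly visit, unless the data collection sheet already has it, covering maternal and infant illness, reactions, hospital visits and deaths since the last visit. State in Section 10 how the answers are recorded.
3. Add to the SAP one descriptive table of these events by randomised arm, giving women or infants with at least one event, the number of events, and deaths, with no hypothesis test.

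**Cost.** The fortnightly form needs a small change. The question has several parts, so field staff need brief training, and the change may count as an amendment under Section 12.4. The visits already take place; no committee or extra staff is needed.

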3.1 Thiamine, and thiamine deficiency

Thiamine (vitamin B₁) is an essential water-soluble micronutrient required for energy metabolism (4). Thiamine deficiency remains an under-studied public health issue, recently being called the forgotten disease of Asia (5). There is evidence of suboptimal thiamine intake or status throughout Southeast

Asia, notably in Cambodia (6–11), Laos (5,12–14), and among Karen refugees during their early arrival in the Mae La Camp on the Thai-Myanmar border (15,16).

Infantile beriberi, a disease caused by thiamine deficiency, presents during the exclusive breastfeeding period and without treatment can result in death within hours of clinical presentation (15). The dietary staple of Cambodia is B-vitamin poor, white, polished rice; it makes up upwards of 60% of daily energy intake (17). Women with poor dietary thiamine intake produce milk low in thiamine, putting their exclusively breastfed infants at a high risk of developing infantile beriberi (18). We recently demonstrated that maternal consumption of a thiamine-fortified fish sauce significantly increased maternal, human milk, and infant thiamine status (10).

There is also a growing body of evidence suggesting thiamine deficiency not severe enough to cause clinical symptoms has a negative effect on cognitive development and functioning (19–22), though the precise pathways and mechanisms linking these two factors remain poorly understood. Important questions remain about the timing of deficiency, levels of deficiency, and the ability of prophylactic interventions to prevent or therapeutic interventions to remediate the effects of suboptimal thiamine status on cognitive outcomes in humans (23).

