8.2 Eligibility criteria

All women must provide written informed consent to participate. Participants must meet the following criteria:

- mothers of a newborn
- aged 18-45 years
- most recent pregnancy was normal (i.e. no known chronic conditions, preeclampsia, gestational diabetes etc.), and the singleton infant was born without complications (e.g. low birth weight (<2.5 kg), tongue tie, cleft palate)
- intends to exclusively breastfeed for six months
- resides in Kampong Thom province, Cambodia, and is not planning to move in the next six months
- is not currently taking, and hasn't taken any thiamine-containing supplements over the previous 4 months
- is not currently participating in any nutrition programs beyond normal care
- is willing to consume one capsule daily from 2 weeks through 24 weeks postpartum
- is willing for her entire household consume only salt provided by the study team
- is willing for the following biological samples to be collected: a maternal venous blood sample and human milk sample at 2 weeks postpartum, a human milk sample at 4 and 12 weeks postpartum, and maternal and infant blood samples and a human milk sample at 24 weeks postpartum

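### Section 10's reasons for having no clinical outcomes to monitor do not cover infant beriberi on 0 mg; beyond a general doctor route and emergency unblinding, no symptom prompt or referral step is described

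*Combined protocol and SAP*

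**What the plan says.** Section 10 of the protocol explains why there will be no serious adverse events committee or data safety monitoring board. It gives three reasons: no harm from thiamine has been reported; "There are also no clinical outcomes for which to monitor: the primary outcome of the study is a biochemical measure of thiamine status", with results known only at the end; and batch analysis leaves nothing to look at mid-study. Section 2.6 sees no need for either body "in the current study because of the absence of potential adverse effects". Section 8.4, on unblinding, adds: "Note that the likelihood of any adverse events is extremely unlikely since there is no UL for thiamine".

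The background takes a different view of the untreated state. Section 3.1 says that low maternal intake lowers the thiamine in milk, "putting their exclusively breastfed infants at a high risk of developing infantile beriberi", and that the disease "presents during the exclusive breastfeeding period and without treatment can result in death within hours of clinical presentation". Section 8.2 requires that the mother "intends to exclusively breastfeed for six months" and has taken no thiamine supplement in the previous four months. One arm in four receives 0 mg.

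The plan has real safeguards. Section 10 says "the study will employ a Cambodian medical doctor from the Kampong Thom Operational District to answer medical questions from mothers" and to look into adverse events ad hoc. Section 8.4 allows unblinding in a medical emergency. Section 9.10 says "All participants will receive a mobile phone and mobile phone credits". Section 6.4 keeps the same field worker with each mother and adds a weekly call. Sections 9.4, 9.5 and 9.9 place general health questions, infant measurements and infant examinations at 2, 12, 24 and 52 weeks.

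**The concern.** All the stated reasons concern either the harm of taking thiamine or the availability of laboratory results. Neither bears on the infant of a mother who takes none. For that infant the hazard is the deficiency disease that motivates the trial. It is a clinical event, visible at the bedside without any assay, so a biochemical endpoint and batch analysis are no reason not to look for it.

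Infant safety is what is at stake. As described, a hazard that the protocol itself names is left to a mother's unprompted report and to ad hoc follow-up. Sections 2.6 and 10 also forecast infant deaths and attribute them in advance to causes outside the study. With no instruction to consider beriberi, a deficiency death on 0 mg could be recorded as unrelated.

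**Working it through.** This is mainly a comparison of texts, with some arithmetic for exposure and workload.

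1. **Stated reason against hazard.**
   - Safety of thiamine (sections 2.6, 8.4, 10): addresses the three active arms, not 0 mg.
   - Biochemical endpoint and batch analysis (section 10): address interim laboratory data, not a sick infant.
   - Hazard named in section 3.1, repeated as potentially fatal in section 3.7: illness in infants fed low-thiamine milk. No stated reason reaches it.

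2. **Where beriberi appears.** It is in the background and rationale (sections 3.1, 3.4, 3.7) and in reference titles. It is in no visit procedure, withdrawal rule or adverse event text. The fortnightly visit (section 9.2) lists capsules, salt and feeding. The weekly call (section 6.4) encourages capsule use. The examinations in section 9.9 state no clinical action.

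3. **Is low infant intake on 0 mg plausible on the plan's own figures?** Section 7 assumes an average minimum of 136 µg/L in milk; section 3.2 uses 780 mL of milk a day. 136 × 0.780 = 106 µg, or 0.106 mg/day, against an adequate intake of 0.2 mg/day. Section 3.2 calls the evidence for that adequate intake poor, so this shows direction only.

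4. **Exposure on 0 mg.** 80 infants × 22 weeks = 1,760 infant-weeks, before attrition.

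5. **The plan's death forecast.** Section 2.6 gives 1.67 to 3.68 infant deaths.
   - Lower end: 0.029 × 0.18 × 320 = 1.67, which reproduces.
   - Upper end: 0.011 × 320 = 3.52, not 3.68.
   - Pro rata on 0 mg (× 80/320): 0.42 to 0.88.

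   These are forecast deaths from other causes, not beriberi deaths. The anchor is weak: the upper rate covers birth to one year rather than 22 weeks, and the infant rate as printed (11 per 1,000) is below the neonatal rate (29 per 1,000), which cannot hold under the definitions given.

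6. **Beriberi incidence.** The documents give none. With p the assumed risk per infant on 0 mg, the chance of at least one case is 1 − (1 − p)^80. For p = 0.5%, 1%, 2% and 5% this is 33%, 55%, 80% and 98%. The range is too wide to support a forecast.

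7. **Workload of one illness question per fortnightly visit.**
   - Visits: 22/2 = 11 per dyad; 11 × 320 = 3,520 answers at full attendance.
   - Referrals if an assumed 2% to 10% of answers lead to one: 3,520 × 0.02 = 70; 3,520 × 0.10 = 352.
   - Calendar time: five months of recruitment (about 21.7 weeks) + 22 = 43.7 weeks.
   - Rate: 70/43.7 = 1.6 a week; 352/43.7 = 8.1, about 8 a week.
   - Asking at each of 22 weekly calls as well: 33 × 320 = 10,560 answers and 211 to 1,056 referrals. That is not proposed.

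**The case against.** The strongest reply is that the challenged sentence is an argument about a monitoring board: no outcome data will exist for interim review. It is not a rule on the care of sick infants, and the next paragraph of section 10 supplies a local doctor. With phones, weekly calls, a familiar field worker, repeated infant examinations and emergency unblinding, a general route to help does exist. This stands. A reader might infer that a sick infant on 0 mg has no route to care or that the plan sets out to ignore illness; the documents support neither. What is missing is anything that prompts suspicion of this disease or says when to refer.

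A second reply is that the relevant advice may lie in material not shown. The SAP preface cites questionnaires and consent forms, and these could tell mothers whom to call and when. That also stands, so the operational parts of the fix are conditional on it. It does not repair the one-sided reasoning in section 10, which is visible.

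A third reply is that a fortnightly question will mostly miss an illness that can kill within hours. This is correct, and it is why the reminder to phone matters more than the question.

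**Conclusion.** The point holds in a limited form. The safety rationale in sections 2.6, 8.4 and 10 omits deficiency illness in infants on 0 mg, a hazard that section 3.1 calls high risk and rapidly fatal. Apart from the general doctor route and emergency unblinding, the visible text gives no beriberi symptom prompt or referral step. The planned exposure is 80 infants and 1,760 infant-weeks.

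A reader might go further and infer that beriberi cases are to be expected on 0 mg, that the placebo arm is untenable, that a monitoring board is required, or that the dose estimate or infant comparisons are biased. The documents support none of these. They give no incidence, and the forecast of 0.42 to 0.88 deaths on 0 mg is for other causes. Nothing shown links the gap to the estimates. Early closure under section 12.6 can already be read to cover placebo, so no change is asked there.

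This is a worthwhile, inexpensive improvement on infant-safety grounds, held with medium confidence because the forms and consent material were not available.

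**What to change.** Amend section 10 to name suspected infantile beriberi as a safety event in all arms, since field staff are blinded.

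Unless the forms or consent material already do so:
- add one infant-illness question to the existing fortnightly visit, with a short criterion, set by the study doctor, for prompt referral to that doctor;
- at existing visits and weekly calls, remind mothers to phone the doctor at once if the infant is ill.

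Have the doctor consider beriberi when reviewing any infant death instead of presuming it unrelated. Report suspected beriberi and infant deaths by arm; deaths may already appear in the flow diagram of section 8.5. How a suspected case is treated is for the sponsor to decide.

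The cost is a few lines in section 10, slightly longer visits, a one-line reminder and one short table. The main downside is extra referrals to a single doctor, about 1.6 to 8 a week under the assumed 2% to 10%, which the referral criterion would help to contain. No new visits, board or stopping rule is needed.
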